
State of the art: Depression in association with acute coronary syndromes (ACS) is an independent risk factor for subsequent cardiac events and mortality. However, the only randomised behavioral intervention trial attempting to reduce cardiac risk in depressed ACS patients showed that changes in depression did not translate into improved survival. Such intervention did not address issues such as lifestyle modification and improvement in psychological well-being, which were found to affect individual vulnerability to medical disease. Our research group has developed a well-being enhancing psychotherapeutic strategy, well-being therapy (WBT), which has been validated in a number of controlled clinical trials.
 
Objective and rationale: To evaluate the efficacy of cognitive behavioral treatment (CBT) with WBT in improving depressive symptomatology and well-being, as well as reducing cardiac risk in depressed and/or demoralized ACS patients compared to clinical management (CM). The same protocol will be carried out in two centres (Bologna and Torino).
 
Experimental plan: 100 patients after a first episode of ACS, meeting DSM-IV criteria for depressive disorders and DCPR criteria for demoralization will be randomized to one of two treatment groups: 1) CBT supplemented by WBT; 2) CM. In both groups, treatment will consist of twelve, 45-minute sessions once a week. A two-year follow-up will be performed.
 
Expected results and their relevance: It is expected that psychological treatment may significantly decrease psychological distress, cardiac morbidity and mortality at follow-up compared to clinical management. The findings may entail considerable preventive implications and possible large reductions in health costs.
				

## RESEARCH PLAN

### Background and rationale

Cardiovascular diseases are the leading cause of death and disability in Europe. Acute coronary syndromes (ACS), such as myocardial infarction and unstable angina, are comorbid with major depressive disorder (APA, 2000) almost 20% of the time. Depression is more than transitory psychological distress: the period of sadness or lack

of interest is abnormally intense or abnormally long and interferes with a variety of personal, interpersonal and social activities. Most patients with depression during the initial ACS hospitalization continue to have depression 1 to 4 months later. Depression impairs health status more than heart disease itself and it is also associated with poor long-term psychosocial outcomes. Several studies suggest that major depressive disorder, and minor depression, that do not meet the criteria for a diagnosis of major depressive disorder, in addition to their effects on quality of life, are risk factors for recurrent events in patients with established cardiac disease (Barth et al, 2004; Rafanelli et al, 2006, 2007). Several prognostic studies have shown that depression is a predictor for survival after ACS (Frasure-Smith et al, 1995) independently of previous cardiac history, cardiac disease severity, or residual left ventricular function. The risk is directly related to the severity of mood symptoms: a 1- to 2-fold increase in ACS for minor depression and a 3- to 5-fold increase for major depression (Bunker et al, 2003; Carney et al, 2008).

Recent studies remark that the classification into diagnostic subgroups of affective disorders is important for an improved clinical and pathophysiological understanding of the relationship with cardiovascular diseases. Dysthymia, a chronic feeling of depression, less intense than major depression, plays an important role regarding this relation. Moreover, dysthymia has shown a stronger association with ACS than unipolar major depression (Baune et al, 2006). In an article by Rafanelli et al (2010), the authors found a prevalence of 13.4% of dysthymia in CHD patients. Among the variables examined as potential risk factors for cardiac outcome events, only dysthymia diagnosis in the years preceding the first episode of CHD attained statistical significance in multivariate analysis (controlled for age, LVEF and absolute cardiac risk).

Recent studies outlined the need to assess different aspects of depression in medically ill patients as well, such as demoralization. This concept has not been defined in current psychiatric nosography. In recent years, psychosomatic research has focused increasing attention on this issue. Psychosocial variables that were derived from psychosomatic research were translated into operational tools by a group of international researchers (Fava et al, 1995), such as Diagnostic Criteria for Psychosomatic Research (DCPR), whereby individual patients could be better diagnosed. Demoralization defined by the DCPR (Rafanelli et al, 2003) is a feeling state characterized by the patient's consciousness of having failed to meet his or her own expectations (or those of others) or being unable to cope with some pressing problems; the patient experiences feelings of helplessness, hopelessness or giving up. Using this definition, a recent study of ACS patients (Rafanelli et al, 2005) revealed that 20% of them were also demoralized. Among patients with major depression, 17% were not demoralized, and among demoralized patients, 7% did not meet the criteria for major depression. The treatment implications of the syndrome of demoralization as defined by the DCPR have not yet been established.

The negative impact of depression on post-ACS prognosis underscores the need for interventions to address these problems. Although antidepressants are effective in reducing depression in ACS patients (Frasure-Smith et al, 2006), their use in cardiac patients remains controversial. Moreover, the SADHART study (Glassman et al, 2002) tested the SSRI sertraline against placebo but found no significant differences in outcome over the 24 weeks of the trial. On the other hand, cognitive behavioral therapy (CBT) is a brief well-established and effective treatment for depression. Over 75% of patients show significant improvements. In earlier clinical trials, CBT has been found to

be as effective as imipramine in the treatment of depression. In addition, this approach has been found superior to other approaches and has been shown to be an effective treatment for depression for older adults and for those with severe depression. As relatively brief goal-oriented, collaborative, and emotionally supportive forms of treatment, cognitive-behavioral is generally well accepted by cardiac patients. Even though the only randomized behavioral intervention trial attempting to reduce morbidity and mortality in depressed patients with existing coronary disease (ENRICHD study) showed that changes in depression did not translate into improved survival, there remains the need to further investigate if treating depression can reduce the risk of morbidity and mortality in ACS patients.

In addition, an extensive body of evidence suggests the influence of psychological well-being in altering individual vulnerability to disease or quality of life. Ryff and Singer (1996) remark that, historically, mental health research is dramatically weighted on the side of psychological dysfunction and health is equated with the absence of illness rather than the presence of wellness. In a naive conceptualization, yet the one implicitly endorsed by the traditional psychiatric nosography, well-being and distress may be seen as mutually exclusive (i.e. well-being is lack of distress). According to this model, well-being should result from removal of distress. Yet, there is evidence both in psychiatric and psychosomatic research to call such views in question. Carol Ryff's multidimensional model of psychological well-being includes environmental mastery, personal growth, purpose in life, autonomy, self-acceptance and positive relations with others (Ryff, 1986). Ryff and Singer discussed the contours of positive human health, and how it is rooted in a biopsychosocial consideration of the patient. Since psychological well-being seemed to alter individual vulnerability to disease or quality of life, it has been found that therapy specifically addressed to the various aspects of well-being has yielded clinical benefits in improving quality of life in chronic and life-threatening illnesses. Well-being therapy, developed by GA Fava (1999), is a short-term, well-being-enhancing psychotherapeutic strategy based on Carol D. Ryff's model. It may be applied as an additional ingredient of cognitive behavioral packages. The first validation studies appeared to be promising (Fava et al, 2006).

### **Specific aims and preliminary findings**

The specific aims of this project are to 1) assess, by reliable methods, the presence of DSM-IV mental depression (major and minor, chronic and acute) and DCPR demoralization in patients with a first episode of ACS; 2) evaluate the efficacy of CBT in combination with WBT and lifestyle modification versus standard CM in reducing psychological distress and improving well-being scores after treatment; 3) evaluate the efficacy of CBT in combination with WBT and lifestyle modification versus CM in reducing the risk of morbidity and mortality in depressed and/or demoralized patients after a first episode of acute myocardial infarction or unstable angina. A two-year follow-up of the patients' population will be performed.

The first validation studies on the application of sequential treatment of CBT with WBT and lifestyle modification in the residual phase of recurrent depression were carried on by the coordinator's group of research (Fava et al, 1998a, 1998b). The results appeared to be promising. The sequential approach has in fact yielded significant advantages in terms of relapse rates and number of episodes of depression, and has resulted in

enduring remission during a drug free state in the majority of patients during a six-year follow-up. Patients who received such treatment reported a substantially lower rate of relapse (40%) during the 6-year follow-up than the patients assigned to clinical management (90%). Such difference was significant, both in terms of comparison of mean survival time and survival analysis (Fava et al., 2004). The findings have dramatically outlined the importance of psychotherapy and clinical psychology in the prevention of relapse in recurrent depression. The sequential approach has been subsequently applied with success also in the U.K. (Paykel et al., 1999; Teasdale et al., 2000), Canada (Ma & Teasdale, 2002) and Netherlands (Bockting et al., 2005). A multicentre randomized controlled trial employing the PI's protocol is currently in progress in Germany. The findings of this sequential strategy have achieved further importance in view of the disappointing results of the U.S. mega-trial STAR\*D, which has predominantly used sequenced pharmacological strategies (Rush et al., 2006). We assume that the combination of CBT and WBT, including lifestyle modification, may yield more profound and enduring effects on psychological distress, cardiac morbidity and mortality than CBT alone.

*Endpoints.* As the primary end-point, the present research includes the improvement in depression as assessed by variations in overall CID score of at least 4.1 points, after CBT-WBT versus CM. The expected superiority of CBT-WBT versus CM is set to the 80%, at, if the pre/post treatment difference of CID scores is at least 4.1 points (Fava et al., 1998b). As secondary end-points the study includes: 1) the improvement of psychological distress and well-being evaluated through the variations in the overall Symptom Questionnaire (SQ) and Psychological Well-Being scales (PWB) scores; 2) the decrease of stress biomarker after CBT-WBT versus CM; 3) the reduction of cardiovascular major adverse events (cardiac mortality, recurrent heart attack and new hospitalization for cardiovascular causes) after CBT-WBT versus CM.

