Both before and after psychological treatment, among laboratory testing, the following biomarkers will be investigated: urinary cortisol excretion, blood DHEA-S level, blood glycosylated haemoglobin, coagulation/fibrinolysis markers, urinary norepinephrine, urinary epinephrine. The association of these biomarkers with stress increases health risk, regardless of the presence of psychiatric disorder (Lupien et al, 1998). Among blood laboratory testing, hyperhomocysteinemias levels will be also detected, since elevated homocysteine metabolism was established as an independent risk for vascular disease (the risk increase directly with total homocysteine level 6% to 7% for every 1  $\mu$ mol/liter increase in total homocysteine level) (Folstein et al, 2007). Heart rate variability (HRV) will be also investigated. Decreased HRV, in fact, a predictor of mortality, is reduced in patients with major depressive disorder after ACS (Glassman et al, 2007). Moreover, markers of pathophysiological mechanisms implicated in ACS will be investigated since they provide incremental value over existing ischemic biomarkers. Systemic markers of inflammation such as elevated C-reactive protein (CRP) levels (Morrow et al, 1998) will be studied for its prognostic value (Biasucci et al, 1996).

Before and after psychological treatment, and then after 3, 6, 9, 12, 18 and 24 months the differences between the two groups in CID, SQ and PWB scores will be analyzed.

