## STATISTICAL PLAN

The sample size was calculated based on the results of previous studies carried out by the Coordinator of the present project. According to the statistical analyses performed in previous studies focusing on treatment efficacy (Fava et al, 1998), a sample size of 100 patients (50 per treatment group) seems appropriate. In the present study, to obtain the

same difference between the mean CID scores with a power of 80%, at least 16 subjects per arm are required according to calculations performed with the piface software (Lenth, 2001, 2006-2009). Multivariate ANOVA will be used to examine differences in dimensional psychological variables (i.e. CID total score, SQ and PWB scales scores) between patients assigned to CBT-WBT and CM at pre-intervention. Mixed-model ANOVA (Repeated Measures) will be performed to test differences between groups (CBT-WBT or CM) on the CID total score, the PWB scales, and the SQ scale scores at different follow-up evaluations. For the comparison between the means of the two groups (CBT-WBT vs CM) in the scores of psychological measures (CID, SQ e PWB) and in the values of the biomarkers, analysis of the covariance will be used, considering baseline scores as covariates. The missing data will be analyzed with the Intention-To-Treat procedure. Survival analysis will be used in order to evaluate the period of time occurred between baseline and new negative cardiac outcomes. The follow-up time considered for relapse will be 24 months after the end of the treatment. Survival analysis will be used for time until relapse into cardiac events. Among factors investigated as possible predictors of outcome, assignment to CBT in combination with WBT or to CM will be included. The Kaplan-Meier method will be used for estimating survival curves. When relapse is the event of interest, survival will be referred to relapse-free status. The log-rank test and Cox proportional hazards model will be included to compare any survival distributions for each of the factors considered. For all tests performed, the significance level will be set at 0.05, two-tailed.

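### The biomarker secondary endpoint names no marker and no success rule, while six to nine candidate markers are open to testing at an unadjusted 0.05

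*Combined protocol and SAP*

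**What the plan says.** Under Specific aims and preliminary findings, the Endpoints paragraph gives the second of three secondary endpoints as "the decrease of stress biomarker after CBT-WBT versus CM". It names no marker, composite or success rule.

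Study design and methods lists the laboratory tests taken before and after psychological treatment: "urinary cortisol excretion, blood DHEA-S level, blood glycosylated haemoglobin, coagulation/fibrinolysis markers, urinary norepinephrine, urinary epinephrine". The next sentence ties that list to stress: "The association of these biomarkers with stress increases health risk". Three more measures follow, each for a different stated reason:

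- homocysteine ("hyperhomocysteinemias levels will be also detected"), as a vascular risk factor;
- HRV ("Heart rate variability (HRV) will be also investigated"), with the remark "Decreased HRV, in fact, a predictor of mortality";
- CRP, as an example of an inflammation marker, for its prognostic value.

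The Statistical Plan says that for group comparisons of the psychological scores and "in the values of the biomarkers, analysis of the covariance will be used, considering baseline scores as covariates". It does not list the biomarkers. It also states: "For all tests performed, the significance level will be set at 0.05, two-tailed".

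Time schedule of the project has urinary and blood biomarkers of cardiac prognostic value measured before and after treatment. It mentions HRV only in the assessment at hospital admission.

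**The concern.** A declared endpoint should tell the reader in advance which result would meet it. This one does not. Several markers are analysed, each at 0.05, and nothing links them to a single conclusion. An analyst who followed the plan exactly could report the endpoint as met on the strength of any one marker, chosen after the results were known.

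The direction is also incomplete. Decrease is the only direction given, and the plan does not state which direction is favourable for each of the six stress-linked markers. For HRV, the protocol's own remark makes a decrease the adverse direction, so it matters whether HRV belongs to the endpoint.

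This is the only biological measure among the secondary endpoints, and a positive result would be read as support for a pathway from psychological treatment to cardiac risk. A chance finding here would carry weight in interpretation.

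**Working it through.** **The plan's own figure.** The documents give no power or error rate for the biomarker endpoint. The only computed design figure is at least 16 per arm for CID, at 80% power and a 4.1-point difference. No SD is given, so it cannot be confirmed. It implies an SD of about 4.0 (t-test) to 4.1 (normal approximation). Nothing below depends on it.

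**How many markers.**

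| Reading | Markers | Count |
|---|---|---|
| Explicitly before/after and tied to stress (Study design and methods) | cortisol, DHEA-S, glycosylated haemoglobin, coagulation/fibrinolysis, norepinephrine, epinephrine | 6 |
| Adding other blood markers (Time schedule of the project) | plus homocysteine and CRP | 8 |
| Adding HRV | plus HRV | 9 |

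The coagulation/fibrinolysis item is plural in the protocol but counted once here, so the number of tests could be higher.

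**Chance of at least one significant difference, either direction, when no marker truly changes.** For k independent tests at 0.05 this is 1 − 0.95^k:

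- k = 6: 1 − 0.95^6 = 26.5%
- k = 9: 1 − 0.95^9 = 37.0%

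**Chance of at least one false difference favouring CBT-WBT.** With one favourable direction fixed per marker, each two-tailed 0.05 test contributes 0.025, giving 1 − 0.975^k:

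- k = 1: 2.5%
- k = 6: 1 − 0.975^6 = 14.1%
- k = 9: 1 − 0.975^9 = 20.4%

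**Allowing for correlation.** The documents give no correlations between markers, so a range is assumed. The figures come from simulating normal test statistics with a common correlation, each marker oriented so that its favourable direction is positive.

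| Assumed correlation | Any difference, k = 6 | Any difference, k = 9 | False benefit, k = 6 | False benefit, k = 9 |
|---|---|---|---|---|
| 0 | 26.5% | 37.0% | 14.1% | 20.4% |
| 0.3 | 24% | 33% | 12% | 16.5% |
| 0.5 | 21% | 27% | 10% | 13% |
| 0.8 | 14% | 17% | 7% | 8% |

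For one named marker the corresponding figures are 5% and 2.5%.

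**What adjustment would cost.** Holm's first step uses 0.05/k: 0.0083 for k = 6 and 0.0056 for k = 9. With 50 per arm and no baseline adjustment, the standardized difference detectable with 80% power is (z for the two-sided level + 0.842) × √(2/50):

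- level 0.05: (1.960 + 0.842) × 0.2 = 0.56
- level 0.0083: (2.638 + 0.842) × 0.2 = 0.70
- level 0.0056: (2.773 + 0.842) × 0.2 = 0.72

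For an assumed effect of 0.6 SD (not in the documents), ANCOVA raises the effective difference to 0.6/√(1 − r²), where r is the assumed correlation between baseline and post-treatment values. At r = 0.5 this is 0.6/√0.75 = 0.69. Noncentral-t power with 50 per arm:

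| Assumed r | Unadjusted 0.05 | Holm first step, k = 6 | Holm first step, k = 9 |
|---|---|---|---|
| 0 (no baseline adjustment) | 84% | 62% | 57% |
| 0.5 | 93% | 78% | 73% |
| 0.7 | 99% | 93% | 91% |

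**The case against.** The best defence is that the endpoint is loosely worded but not misleading. The later sections all speak of biomarkers in the plural, so the singular is probably loose English and not a sign that one marker was chosen and then withheld. The endpoint is secondary, biomarkers do not appear in the numbered specific aims, and the primary CID result does not depend on them. All of that stands, and it limits the severity. It does not supply a success rule: reading the endpoint as plural leaves open which markers, how many, and in which direction.

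Four stronger readings are tempting, and the documents do not support them.

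- *Nine or more markers will each be tested.* Nine are named, but the Statistical Plan never lists the tested set. Only six are explicitly measured before and after treatment and tied to stress.
- *A worsening of HRV would count as success.* This needs HRV to be part of the stress-biomarker endpoint, and no section says so. The sentence about stress refers to the six markers before it. The time schedule limits the before/after set to urinary and blood markers. HRV's position in the before/after paragraph makes inclusion a fair reading, not an established one. The protocol's words are also that decreased HRV predicts mortality, not that it is harmful.
- *There is a 37% chance of a false biomarker benefit.* That figure takes nine independent markers and counts differences in either direction, including those favouring CM. The matching figure for a false benefit is 20.4%.
- *The endpoint is invalid.* What the text shows is that no success rule is specified. That can be repaired.

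**Conclusion.** The point holds as a gap in specification with a measurable consequence. The endpoint does not say which marker or result counts, and the plan's rule of 0.05 for every test leaves the choice open until after the data are seen. If no marker truly changes, the chance of at least one false difference favouring CBT-WBT is 14.1% (six markers) to 20.4% (nine) under independence, and about 10% to 13% at an assumed correlation of 0.5. For one named marker it is 2.5%. Even six markers at a correlation of 0.8 give about 7%.

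The range depends on two things the documents do not settle: which markers form the endpoint, and how strongly they are correlated. The conclusion that error is inflated does not depend on HRV, since it already holds for the six explicit markers. This should be corrected, but the primary CID conclusion is untouched.

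**What to change.** In the Endpoints paragraph, list the markers that form the endpoint and state the beneficial direction of each. Break the coagulation/fibrinolysis item into the specific assays intended. State whether homocysteine, CRP and HRV belong, and when each is measured. If HRV is included, decrease cannot be its success direction, given the protocol's own remark about mortality.

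In the Statistical Plan, choose one of two rules before the data are seen:

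- name one key marker, chosen by the investigators on scientific grounds, tested at 0.05, with the others labelled exploratory; or
- apply Holm across the listed family, and say that a biomarker benefit is claimed only for markers that pass in the stated direction.

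Both are changes of wording. Neither needs more patients, and neither adds measurements unless the investigators decide to include HRV after treatment and had not planned to measure it then. Under the first rule the named marker keeps full power, but no other marker can support a claim at unadjusted 0.05. Under Holm, first-step power for the assumed 0.6 SD effect falls from 84% to 57–62% without baseline adjustment, or from 93% to 73–78% with the planned ANCOVA at an assumed baseline correlation of 0.5.
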